1.3 Study Rationale

Upamostat will be studied for treatment of patients with symptomatic, PCR- or antigenconfirmed COVID-19. Several findings support the use of upamostat for treatment of COVID-19:

- Analysis of the structure of TMPRSS2 as compared to proteases tested for sensitivity to WX-UK1 suggests that the compound would have a Ki against TMPRSS2 in the high nanomolar to low micromolar range ([name], personal communication);
- In vitro data in two experimental systems demonstrate that upamostat inhibits SARS-CoV-2 at noncytotoxic concentrations, concentrations well below that which are achievable clinically;
- The potent trypsin inhibitory effect of upamostat may decrease pulmonary tissue damage and gastrointestinal symptomatology due to infection;
- Decrease in circulating D-dimer by upamostat, demonstrated in experimental systems, may indicate a systematic anticoagulant effect, which may decrease the incidence or severity of thrombotic events in COVID-19 patients.

The primary endpoint of this study is time to sustained recovery from acute COVID-19 disease for all patients. For high-risk patients, the first secondary endpoint is hospitalization or death. In addition, patients will be followed using multiple additional clinical and laboratory assessments over time. Viral shedding is a secondary endpoint. This is of importance in itself, as continuation of viral shedding increases the risk of spread of disease and impacts quality of life as the patient must spend longer in isolation. Decreasing the duration of viral shedding will safely allow patients to resume normal activities earlier than otherwise possible.

Because a) no oral therapy has demonstrated efficacy in treatment of COVID-19, and b) the existing treatments approved for outpatient use under EUA are antibody combinations indicated only for high risk patients and which require availability of facility for infusion therapy, use of a placebo comparator appears justified in the outpatient population in areas in which the antibodies are not available. In addition, many patients opt not to receive antibody infusions despite their availability. Therefore, patients in part B of the study will be stratified and outcomes will be analyzed according to antibody use. Two thirds of patients entered in part A of the study will receive active drug, and in part B, 60% will receive active drug. Randomization 3:2 in part B will provide an incentive for participation in the study: patients will have a 50% greater probability of receiving active drug than placebo. This also provides a larger sample size for evaluation of safety than a 1:1 randomization. Yet the shift from 1:1 to 3:2 randomization increases the overall sample size by less than 10%.

In part A of the study, upamostat will be administered at a dose of either 200 or 400 mg daily. While both dose levels have been tolerated well in oncology studies, it appears

prudent to test two dose levels in this new population. If both are tolerated similarly, the higher dose will be used in part B of the study. If there are differences in tolerability, absent clinically significant differences in efficacy, the lower dose will be used in part B.

As an early indication of pharmacologic activity, six parameters found to be associated with severity and outcome of COVID-19 disease will be assessed at multiple time points during the study: oxygen saturation, C-reactive protein, lymphocyte counts, D-dimer, troponin and ferritin levels. The primarily pharmacodynamic parameters, CRP, troponin and ferritin, will be followed only in territories in which they are readily available through a central lab which can standardize the results across sites. Those analytes which are also safety parameters, oxygen saturation, D-dimer and lymphocyte counts, will be followed in all patients.

Under this amendment, the study procedures have been modified taking into account experience with the first patients entered into the study, as well as reasons patients have declined to participate. To date, symptoms have resolved in one to under three weeks. Patients have been resistant to the heavy monitoring and questioning in the original protocol, resulting in reluctance to participate in the study, withdrawal of several patients and poor compliance with study procedures. In order to enhance acceptability, accrual and compliance with the protocol, the duration of intensive vital sign monitoring is being reduced. In addition, the definition of sustained recovery is modified to take into account the patient compliance issue and experience to date with those patients who have recovered. If a substantial proportion of patients withdraws prior to the end of study *because* they feel better and the burden of study procedures is excessive, their efficacy results will be censored and those patients will be declared nonresponders. Temperature will be followed through 28 days after resolution of fever, if the patient is febrile, but with lower frequency from day 15 onward after resolution of fever.

Hospitalization or death has been moved to become the first secondary endpoint. FDA views this endpoint as that for which potential emergency use authorization is justified.

2. Objectives

Primary

Part A of the study: determination of the safety and tolerability of two dose levels and selection of an upamostat dose for part B. Part B of the study:

Primary objective: in the entire patient population, comparison between upamostat and placebo in time to sustained recovery from symptomatic illness in all patients. A patient will be considered to have recovered once he or she meets the following criteria:

- 1) is afebrile (<38.0° C core temperature) for at least 48 hours without use of antipyretics;
- 2) all symptoms have resolved or returned to pre-illness levels (e.g., if patient had respiratory compromise prior to the onset of COVID-19), except for:
 - i. fatigue, anosmia, ageusia or dysgeusia, which may be persistent at a level similar to that during the acute illness, i.e., the same level per symptom questionnaire;
 - ii. chest pain, cough or dyspnea, which if persistent must be at least one grade lower than at the start of treatment and no worse than grade 1 (mild).

Sustained recovery is recovery, per above definition, maintained for at least 14 or 28 days, or through end of study, whichever comes first. The period required to confirm sustained recovery, 14 versus 28 days, will be assessed in part A of the study and a decision reached as to which period to use for definition of sustained recovery in part B.

Symptoms to be followed and their grading are given in Appendix 2, Patient Diary.

Secondary:

Comparison between active and placebo of:

- 1) Hospitalization or death from any cause by end of study, i.e, day 57. The definition of high risk may be adjusted after part A and at the interim analysis in part B based on the incidence of hospitalization or death found in patients initially entered in the placebo group.
- 2) In part A and at the interim analysis in part B, assessment of the risk of hospitalization or death as a function of the presence, number and severity of concerning conditions will be undertaken. This information may be used to develop a definition of very high risk for calculation of the incidence of hospitalization or death in part B.
- 3) Proportion of patients who are PCR-negative at days 8, 15, 29 and 57 from the start of treatment (landmark analyses)
- 4) Time to resolution of individual disease-related symptoms present at baseline;
- 5) Development of new disease-related symptoms and/or pneumonia on study;
- 6) Changes in laboratory markers of disease severity, i.e., oxygen saturation, CRP, lymphocyte count, cardiac troponin, and D-dimer levels, from baseline to time points at which these are measured on study;
- 7) Adverse events.

In addition to analysis within the entire study population, subgroup analyses for secondary endpoints 1, 3-6 will be performed in the high risk population. Analysis for secondary endpoint 1 will focus primarily on the high risk and very high risk subgroups.

Exploratory

- 1) Percent of patients who have household contacts who have developed symptomatic, PCR or antigen-confirmed COVID-19 by day 57;
- 2) Levels of serum IgM and IgG antibodies to SARS-CoV-2 at 57 days from the start of treatment.

3. Study Population

A total of approximately 310-435 patients will be entered in this study.

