This is a 2-part, multicenter, Phase 2/3, randomized, double-blind, placebocontrolled, parallel group study to evaluate the safety and efficacy of upamostat in adult patients with COVID-19 disease. The primary objective at the end of part A, after 60 patients have completed the study (defined in Section 4.5), is dose selection. An analysis of part A will be performed by a data safety monitoring board (DSMB) who will determine, based primarily on safety results, if the study should proceed to part B and, if so, which dose to proceed with. For part B, the primary endpoint is time to sustained recovery from illness in the entire study population and the first secondary endpoint is incidence of hospitalization or death during the eight-week study period among the high risk patients. The target sample size in part B will be determined at the end of part A but will be at least 250 patients. An interim analysis for adjustment of criteria for high risk, early termination for futility or increase in sample size (to an additional 50% of the initially planned total) will be performed after approximately half of the initially planned patient population has reached end of study; the timing of the interim analysis may also be adjusted at the end of part A.

Rationale:

COVID-19 is a disease caused by a recently discovered coronavirus, designated SARS-CoV-2. It is highly contagious and generally causes fever and respiratory symptoms in symptomatic individuals; additional symptoms are gastrointestinal, cardiac, taste and smell abnormalities, and neurological. The disease spectrum varies from asymptomatic infection through fatal pneumonia and multiorgan failure. Males, older adults and individuals with significant comorbidities, including respiratory diseases, diabetes, obesity and cancer under treatment, are most severely affected.

One medication, remdesivir, has shown efficacy in treatment of COVID-19 in hospitalized patients with severe illness; several monoclonal antibody combinations have demonstrated preliminary evidence of efficacy in the outpatient setting as well. Based on CDC data (CDC, 2020), fewer than 10% of COVID-19 patients are hospitalized. Therefore, an oral, room temperature stable, easily administered medication for treatment of COVID-19 is a major unmet medical need and can be used for both inpatients and outpatients.

Upamostat, a serine protease inhibitor, is a potent inhibitor of trypsin and trypsinrelated enzymes.

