This is a randomized, double-blind, placebo-controlled, parallel group study of upamostat compared to placebo in patients with symptomatic COVID-19 who do not require immediate treatment with specific approved (either fully approved or available under emergency use authorization) antiviral or anticytokine therapy, other than therapeutic monoclonal antibodies. The study uses phase 2/3 operationally seamless design methodology for dose selection (part A) and inferentially independent confirmatory phase 3 study (part B). The phase 3 portion will include an interim analysis for revision of the high risk/very high risk subgroup definition, early termination for futility or increase in sample size, as indicated by initial results.

Methodology:

Part A: After qualification for study, patients will be stratified by age, <65 or ≥65, and randomized to treatment as described below. They will then be randomized 1:1:1 to one of the following treatment groups:

- 1. Upamostat 200 mg two capsules qd (n=20);
- 2. Upamostat 200 mg one capsule and matching placebo one capsule qd (n=20)
- 3. Placebo two capsules qd (n=20).

In order to maintain blinding, patients will be given two bottles of medication and instructed to take one pill from each bottle each day. Both pills are to be taken at the same time

Medication should be taken with water and may be taken with or without food.

Patients are to take medication for 14 days or until one of the following occurs:

- Adverse events, whether related or unrelated to study medication which, in the judgement of the investigator, necessitate discontinuation of treatment;
- The patient or investigator decides that it is in the patient's best interest to stop treatment.

An analysis will be performed by a data safety monitoring board (DSMB) after a total of 60 patients complete part A of the study.

- If the DSMB determines that safety of both regimens is similar, accrual in part B will proceed with the 400 mg qd dose.
- If safety is more favorable with the 200 mg qd regimen, accrual in part B will proceed with the 200 mg qd dose.

The DSMB process is further defined in the body of the protocol and will be detailed in a separate DSMB charter. While the DSMB will perform the evaluation at the end of part A independent of the Sponsor, the results will be provided when available in open label fashion to the Sponsor.

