All patients who live in regions in which one or more therapeutic monoclonal antibody combinations for outpatient treatment of COVID-19 are available will either be offered antibody, if provided at that facility, or given information as to where they can receive the antibodies. The patient may decide whether or not to take the antibody combination; receipt or refusal of antibody therapy will not affect the patient's participation in this trial. If used, the antibody may be administered before or after the patient starts study medication. However, the patient may not start study medication more than 5 days after onset of symptoms or receipt of laboratory diagnosis of COVID-19, whichever is longer.

In part B, patients will be stratified based on

- 1. The presence of none versus one or more of the above factors,
- Planned receipt vs nonreceipt of therapeutic monoclonal antibodies for COVID-19,
- 3. Region in which patient is treated,

4. Whether the patient is at least 14 days after his or her last dose of COVID-19 vaccine.

and randomized to treatment as described below.

Initially in part B, the proportion of patients in the low risk group, i.e., with no concerning conditions, will be limited to 30%. This number and the definition of high risk, in terms of number and types of risk factors, may be revised at the time of the part A analysis and, in order to enroll a very high risk cohort, again at the interim analysis in part B.

Part A

Initially, a total of 60 patients will be randomized to one of three treatment groups, as follows:

- 1. Upamostat 200 mg two capsules qd (n=20);
- 2. Upamostat 200 mg one capsule and matching placebo one capsule qd (n=20)
- 3. Placebo two capsules qd (n=20).

In order to maintain blinding, patients will be given two bottles of medication and instructed to take one pill from each bottle each day. Both pills are to be taken at the same time.

Part B

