If part B of the study is repowered, the timing of the interim analysis may be adjusted. At the interim analysis, the incidence of hospitalization or death in the high risk group, defined as patients with one or more of the concerning conditions listed in Section 4.1, may be modified. A higher risk group may be defined in order to establish an adequate incidence level of hospitalization or death in a well-defined subgroup to ensure the study is adequately powered for the analysis of this endpoint in a meaningful patient population. This may result in a revised sample size and limiting or redefining recruitment in the different subgroups. Sample size reassessment for the primary endpoint will only be conducted if the revised sample size is lower than the maximum sample size proposed for the primary endpoint as above.

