7.2 Analysis Datasets

The primary and most secondary efficacy analyses will be performed on the modified intent to treat (mITT) population, defined as all randomized patients who receive any treatment. A per protocol (PP) analysis will be performed on patients with no major protocol violations and who receive at least one week of study medication or the reason

for stopping medication is worsening COVID-19 or development of AEs. In these analyses patients will be analyzed according to their randomized treatment. Analysis for the first secondary endpoint, hospitalization or death, will be performed primarily on a subset of the mITT population, the high risk or very high risk subset to be defined at the end of part A and redefined at the interim analysis of part B.

Formal efficacy analyses will be performed using part B enrolled subjects, the efficacy data from part A subjects will be descriptively summarized separately.

Safety analyses will be performed on all patients who receive any study medication in parts A and B combined, according to the treatment actually received.

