7.4.2 Analysis of the secondary efficacy endpoints

Comparison between active treatment and placebo of the following secondary efficacy endpoints will be performed:

- 1) Incidence of hospitalization or death: the primary assessment of this endpoint will be among patients in the high risk group. This has been defined preliminarily above. The group may be redefined and recruitment restricted based on analysis at the end of part A and again in the interim analysis of part B. Additional secondary endpoints include:
- 2) The proportion of patients who are PCR-negative at each time point assessed, days 8, 15, 29 and 57 from the start of treatment (landmark analysis);
- 3) Time to resolution of individual disease-related symptoms present at baseline;
- 4) Development of new disease-related symptoms or pneumonia on study:

5) Changes in laboratory markers of disease severity, i.e., oxygen saturation, CRP, lymphocyte count and D-dimer levels, from baseline to time points at which these are measured on study;

The time frame for all endpoints unless otherwise stated is from Day 1 (day of first dose of study medication) through study Day 57. The time to event endpoints will be analyzed using the methods described for the primary endpoint above.

Binary (Yes/No) endpoints (development of pneumonia, hospitalization and mortality) will be summarized using counts and percentages for each group. A 95% confidence interval will be constructed for each proportion. Population-level risk differences will be used to estimate treatment effect. More specific details will be provided in the SAP.

Changes from baseline in continuous variables will be summarized by descriptive statistics and analyzed using repeated-measures model. Data will be log transformed, as needed.

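### The high-risk group may be redefined at the part B interim from placebo-arm hospitalization/death, and nothing controls the resulting tilt toward the drug

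*Protocol*

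**What the plan says.** Hospitalization or death by day 57 is the first secondary endpoint of part B and is assessed mainly in the high-risk or very-high-risk subgroup. That subgroup is not fixed.

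- Protocol section 2, Secondary 1, permits two changes to the definition: one once part A is done, and a second "at the interim analysis in part B based on the incidence of hospitalization or death found in patients initially entered in the placebo group". This is the only place that names the placebo arm as the basis. Section 4.8 comes close: for a repowered study it aims at an expected rate of 15% or more in the high-risk control group.
- Section 4.1 lets "the definition of high risk, in terms of number and types of risk factors" be revised after part A and, "in order to enroll a very high risk cohort, again at the interim analysis in part B". Condition types are therefore open to choice as well as a count.
- The synopsis announces "An interim analysis for adjustment of criteria for high risk" and, under Design, "an interim analysis for revision of the high risk/very high risk subgroup definition".
- Section 7.2 analyses the endpoint in a subset of mITT "to be defined at the end of part A and redefined at the interim analysis of part B". Formal efficacy analyses use part B patients, and no exclusion of pre-interim patients is stated.
- Section 7.4.2 allows the same change: "redefined and recruitment restricted based on analysis at the end of part A and again in the interim analysis of part B". Section 7.1 adds, for a repowered study, "limiting or redefining recruitment in the different subgroups".
- Section 7.4.3 bases error control on keeping part A data separate, the promising zone, no early stopping for efficacy, and a hierarchy gated by the primary endpoint. SAP 4.4 repeats the part A argument and the hierarchy. Neither mentions redefining the tested population.

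The SAP covers part A; SAP 1 says a part B SAP will follow. The passages on redefinition in SAP 3 and SAP 13 place it after part A only, while the SAP Study Summary, SAP 5.4 and the end of SAP 3 keep a part B interim step.

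**The concern.** Redefinition after part A is harmless to part B, because part A patients are not in the part B analysis. Redefinition at the part B interim is different. The placebo outcomes that guide the choice appear to be analysed again in the chosen subset; this reuse is inferred from section 7.2, not stated there. Subgroups in which placebo did badly by chance are favoured, and the active arm undergoes no matching selection.

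None of the protections in section 7.4.3 reaches this. The primary-endpoint gate limits false claims when the drug affects neither endpoint. It does not help when recovery truly improves and hospitalization or death does not, and it cannot correct an estimate.

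Protocol section 1.3 says the FDA regards this endpoint as the one that could justify emergency use authorization. An overstated risk difference in the selected subgroup could therefore carry weight even when the primary result is sound. The whole-population analysis, also planned in section 2, is unaffected.

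**Working it through.** **1. The plan's own figure.** With hazard ratio 1.5, 3:2 allocation, 80% power and two-sided 0.05 (section 7.1), Schoenfeld's formula gives (1.960 + 0.842)² / [0.6 × 0.4 × (ln 1.5)²] = 7.85 / 0.0395 = 199 events, against 201 stated. Then 201 / 0.80 = 251 patients, against 250. The stated design reproduces. The documents give no error rate for a redefined subgroup, so that was simulated.

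**2. Information at the interim.** Section 4.1 puts the interim at about 125 patients. At 3:2 that is 125 × 0.4 = 50 on placebo. At an assumed 8% incidence, 50 × 0.08 = 4 placebo events would guide the choice.

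**3. Simulation with no drug effect on hospitalization/death (900 scenarios).**
- From the protocol: 3:2 allocation; N = 250 or 375 with the interim at 125; the 15% control target if repowered.
- Assumed: overall incidence 6, 8 or 10%; eight independent conditions with prevalences 15, 30, 10, 15, 35, 10, 5 and 5%; risk ratio per condition 1.0, 1.5 or 2.0; a repowered N of 600 or 1,000 with the interim at half.
- Candidate definitions: counts only (≥1, ≥2, ≥3 conditions), or types allowed (≥1 or any single condition, with or without the counts).
- Assumed rule, not repowered: take the highest interim placebo rate, with at least 5 or 10 interim placebo patients; 20,000 trials each.
- Assumed rule, repowered: take the broadest definition reaching 15%, otherwise keep ≥1 or take the highest, with at least 10 patients; 10,000 trials each.
- Test (assumed, since section 7.4.2 names none): pooled two-proportion z-test on all part B patients in the chosen group.

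| Selection | Later enrolment | Candidates | Drug-favouring error (nominal 2.5%) | Spurious benefit, points |
|---|---|---|---|---|
| Fixed, ≥1 condition | – | – | 2.4–3.1% | within 0.1 |
| Placebo, not repowered | restricted | counts | 2.7–3.7% | 0.1 to 0.6 |
| Placebo, not repowered | restricted | types allowed | 3.2–4.9% | 0.4 to 1.7 |
| Placebo, repowered | restricted | counts | 2.6–3.9% | 0.0 to 0.5 |
| Placebo, repowered | restricted | types allowed | 3.2–5.6% | 0.1 to 1.2 |
| Placebo, both sizes | open | counts | 2.7–4.5% | −0.4 to 2.3 |
| Placebo, both sizes | open | types allowed | 3.2–8.2% | 0.5 to 6.9 |
| Pooled, blinded | both | all | 2.2–3.3% | within 0.25 |

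With placebo selection, two-sided error is 4.7–6.6% restricted and 4.1–8.6% open.

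**4. The gate.** Suppose recovery truly improves with 80% power and the two endpoints are independent. The restricted-enrolment errors become 0.80 × 2.62–3.86% = 2.1–3.1% for counts and 0.80 × 3.19–5.63% = 2.6–4.5% with types. A fixed definition gives 0.80 × 2.44–3.12% = 1.9–2.5%.

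**5. A second model.** This used 4 or 8 separate groups or a nested count, true rates 3–20%, 175–375 high-risk patients and a 15% threshold, with 40,000 trials per scenario. Placebo selection gave 3.4–13.0% and 1.3–8.5 points with enrolment open, and 3.3–9.5% and 0.4–3.8 points restricted. Pooled selection gave 2.4–3.0%. Testing only post-interim patients gave 2.4–3.1%. Both of these kept bias within about 0.15 point.

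**The case against.** The strongest reply is that this is an optional step in an unfinished plan. Protocol section 7 says part B analysis revisions will be settled before the part B interim, the SAP provides for later amendments, and a DSMB charter not seen here governs the interim. The placebo basis rests on one sentence, and the 15% target applies only if the study is repowered. This affects how urgent the point is. It does not remove it: the placebo basis stands in the current protocol, sections 2, 7.2 and 7.4.2 do not make redefinition depend on repowering, and sections 7.1 and 7.6 assign the charter rules for sample size, not for redefining risk.

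The objection on size stands in part. The larger figures come from small subgroups. With N = 250, 8% incidence, risk ratio 1.5 and condition types as candidates, results fall as the required number of interim placebo patients rises:

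| Minimum | Restricted: error, bias | Open: error, bias |
|---|---|---|
| 5 | 5.0%, 1.5 points | 6.0%, 6.0 points |
| 10 | 3.9%, 1.0 | 4.5%, 2.5 |
| 15 | 3.4%, 0.6 | 3.9%, 1.3 |
| 20 | 2.9%, 0.2 | 3.1%, 0.3 |

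An assumed latent correlation of 0.3 between conditions lowers the restricted 5.0% to 3.9%. The independence behind the gate figures is also doubtful, because section 7.4.1 counts hospital days as not recovered. Finally, the plan's alpha is two-sided, and two-sided error often stays near 5%.

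**Conclusion.** The concern holds. If the part B interim redefinition follows section 2 as written and pre-interim patients stay in the analysis, the high-risk estimate and the drug-favouring tail generally shift toward the drug, and sections 7.4.3 and SAP 4.4 do not address it. The harm is mainly to the estimate.

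The size depends on a selection rule, candidate list, incidence and condition mix that the documents do not give. The simulated ranges are therefore illustrations, not bounds. With restricted enrolment and counts only, the low ends show no real excess; free choice among condition types with enrolment left open is the worst case in the main model, and other candidate lists can give more. The direction was the same across the models tried, apart from a slightly negative low end (−0.4 point) for counts only with open enrolment. The point should be fixed before the part B interim.

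**What to change.** In protocol sections 2, 4.8, 7.1, 7.2 and 7.4.2 and in the part B SAP, base any part B interim redefinition of the tested population on incidence pooled over both arms and blinded to treatment. Write the selection rule down before the interim, restate any 15% control target on the pooled scale, and say in section 7.4.3 that this is how error is controlled.

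The changes are to wording in the protocol, part B SAP and charter, but each option has a price.

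- **Pooled rule.** If the drug works, the pooled rate sits below the control rate. At 3:2, a 15% control rate corresponds to 15 × (0.4 + 0.6 × 0.7) = 12.3% for an assumed 30% risk reduction, and 15 × (0.4 + 0.6 × 0.5) = 10.5% for 50%. Some overstatement remains when the drug works: 0.1–0.6 point restricted, against 0.4–1.5 with placebo selection, and 0.1–2.0 open, against 0.7–6.2 (8% incidence, N = 250 and 600).
- **Freeze the tested population after part A** and let the interim change enrolment only. The definition then rests on about 20 placebo patients. At 8% incidence that is 20 × 0.08 = 1.6 expected events, and the chance of one or none is 0.92²⁰ + 20 × 0.08 × 0.92¹⁹ = 52% (66% at 6%, 39% at 10%). Section 7.1 itself warns that a part A database is very small.
- **Test post-interim patients only.** This also restores the error rate, but gives up roughly half the part B data for this endpoint.

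Two related items belong in the same revision. Section 4.1 and SAP 3, in a paragraph that opens with the repowered case, let final-analysis stratification or covariate weighting change on interim results. Apply the same blinded, pre-written rule there or remove the permission; its effect was not computed. In the part B SAP, align the part-A-only wording of SAP 3 and 13 with the interim step kept in the Study Summary, SAP 5.4 and the end of SAP 3.
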